3.1.3 Phase 1b

The Phase 1b portion of the study has been described in Section [3.1.1](#).

A total of 6 subjects were enrolled in Phase 1b; this portion of the study is now complete.

3.1.3.1 Dose-exploration Criteria for Phase 1b

Safety Run-in Rules

1. A minimum of 6 subjects will be enrolled in the safety run-in.
 - a. If 2 DLTs occur in the first 6 subjects, an additional 3 subjects will be enrolled.
 - b. If ≥ 3 of 9 subjects experience DLTs, lower dose levels will be evaluated.
2. Dose-limiting toxicity will be evaluated during the DLT evaluation period (as defined in Section 3.1.3.2).

3.1.3.2 Dose-limiting Toxicity

Dose-limiting toxicity will be evaluated during the DLT evaluation period in Phase 1b.

Subjects who do not remain on the study up to this time for reasons other than DLT will be replaced with another subject at the same dose level. Dose-limiting toxicity will be graded according to the National Cancer Institute Common Terminology Criteria for Adverse Events (NCI CTCAE) v4.03.

A DLT will be defined as any Grade 3 or higher toxicity that occurs during the DLT evaluation period. Toxicity that is clearly and directly related to the primary disease or to another etiology is excluded from this definition. The following will be DLTs:

- Any Grade 4 irAE
- Any \geq Grade 3 colitis
- Any Grade 3 or 4 noninfectious pneumonitis irrespective of duration
- Any Grade 2 pneumonitis that does not resolve to \leq Grade 1 within 3 days of the initiation of maximal supportive care
- Any Grade 3 irAE, excluding colitis or pneumonitis, that does not downgrade to Grade 2 within 3 days after onset of the event despite optimal medical management including systemic corticosteroids or does not downgrade to \leq Grade 1 or baseline within 14 days
- Liver transaminase elevation $> 8 \times$ ULN or total bilirubin $> 5 \times$ ULN
- Any \geq Grade 3 non-irAE, except for the exclusions listed below

The definition excludes the following conditions:

- Grade 3 fatigue lasting \leq 7 days
- Grade 3 endocrine disorder (thyroid, pituitary, and/or adrenal insufficiency) that is managed with or without systemic corticosteroid therapy and/or hormone replacement therapy and the subject is asymptomatic
- Grade 3 inflammatory reaction attributed to a local antitumor response (eg, inflammatory reaction at sites of metastatic disease, lymph nodes, etc)

- Concurrent vitiligo or alopecia of any AE grade
- Grade 3 infusion-related reaction (first occurrence and in the absence of steroid prophylaxis) that resolves within 6 hours with appropriate clinical management
- Grade 3 or 4 neutropenia that is not associated with fever or systemic infection that improves by at least 1 grade within 3 days. Grade 3 or Grade 4 febrile neutropenia will be a DLT regardless of duration or reversibility
- Grade 3 or 4 lymphopenia
- Grade 3 thrombocytopenia that is not associated with clinically significant bleeding that requires medical intervention, and improves by at least 1 grade within 3 days
- Isolated Grade 3 elevations in amylase and/or lipase that are not associated with clinical signs or symptoms or radiographic features suggestive of pancreatitis
- Isolated Grade 3 electrolyte abnormalities that are not associated with clinical signs or symptoms and are reversed with appropriate maximal medical intervention within 3 days

Immune-related AEs are defined as AEs of an immune nature (ie, inflammatory) in the absence of a clear alternative etiology. In the absence of a clinically significant abnormality, repeat laboratory testing will be conducted to confirm significant laboratory findings prior to designation as a DLT.

While the rules for adjudicating DLTs in the context of dose escalation specified above, an AE not listed above may be defined as a DLT after a consultation with the sponsor and investigators, based on the emerging safety profile.

3.1.3.3 Maximum Tolerated Dose

The MTD is defined as the highest dose within a cohort where no more than 1 of 6 subjects (or less than one-third of subjects if the cohort is larger than 6 subjects) experiences a DLT. This will be determined during Phase 1b based on the assessment of DLT during the DLT evaluation period, as defined in Section [3.1.3.2](#).

3.1.4 Phase 2

At the time of this amendment, a total of [] subjects have been enrolled in Phase 2 in Arms A [] B [] C [] and D []. Pre-specified interim analyses performed on Arms A and B showed that the criteria for expansion were met; however, enrollment to Arms A, B, and C was stopped at the sponsor's discretion. It was decided to proceed with MEDI4736 in combination with tremelimumab only in second- and third-line subjects with metastatic or recurrent gastric or GEJ adenocarcinoma who had a positive IFN- γ gene expression signature. The discontinuation of Arms A, B, and C was not due to safety concerns. Arm D has completed.

As described in Section 3.1.1, Phase 2 will include the following 5 treatment arms:

- Arm A: MEDI4736 in combination with tremelimumab in second-line subjects with metastatic or recurrent gastric or GEJ adenocarcinoma []
- Arm B: MEDI4736 monotherapy in second-line subjects with metastatic or recurrent gastric or GEJ adenocarcinoma []
- Arm C: Tremelimumab monotherapy in second-line subjects with metastatic or recurrent gastric or GEJ adenocarcinoma []
- Arm D: MEDI4736 in combination with tremelimumab in third-line subjects with metastatic or recurrent gastric or GEJ adenocarcinoma []
- Arm E (as of Amendment 6): MEDI4736 in combination with tremelimumab in second- and third-line subjects with metastatic or recurrent gastric or GEJ adenocarcinoma and a positive IFN- γ gene expression signature []

During Phase 2, subjects will be monitored continuously for safety according to the same criteria employed during Phase 1b. If during the treatment period, $\geq 33\%$ of subjects experience safety events meeting DLT criteria, even if outside of the DLT evaluation period (see Section 3.1.3.2), enrollment may be paused and study data will be reviewed to determine whether additional monitoring or alternate dose levels or treatment schedules should be evaluated prior to further enrollment. In addition, after the first 20 subjects have been dosed with MEDI4736 in combination with tremelimumab for a minimum of 6 weeks (in both second- and third-line settings), safety data will be reviewed by the sponsor.

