- Arm B: MEDI4736 monotherapy in second-line subjects with metastatic or recurrent gastric or GEJ adenocarcinoma [REDACTED]
- Arm C: Tremelimumab monotherapy in second-line subjects with metastatic or recurrent gastric or GEJ adenocarcinoma [REDACTED]
- Arm D: MEDI4736 in combination with tremelimumab in third-line subjects with metastatic or recurrent gastric or GEJ adenocarcinoma [REDACTED]
- Arm E (as of Amendment 6): MEDI4736 in combination with tremelimumab in second- and third-line subjects with metastatic or recurrent gastric or GEJ adenocarcinoma and a positive IFN- γ gene expression signature [REDACTED]

During Phase 2, subjects will be monitored continuously for safety according to the same criteria employed during Phase 1b. If during the treatment period, $\geq 33\%$ of subjects experience safety events meeting DLT criteria, even if outside of the DLT evaluation period, enrollment may be paused and study data will be reviewed to determine whether additional monitoring or alternate dose levels or treatment schedules should be evaluated prior to further enrollment. In addition, after the first 20 subjects have been dosed with MEDI4736 in combination with tremelimumab for a minimum of 6 weeks (in both second- and third-line settings), safety data will be reviewed by the sponsor.

All subjects will be evaluated for clinical activity, on a regular basis as specified in the protocol, and their disease status primarily analyzed according to RECIST v1.1. Clinical decision making in subjects undergoing treatment will be based on RECIST v1.1 with modifications. Enrollment into any arm in Phase 2 may be discontinued at the discretion of the sponsor should emerging clinical or nonclinical data suggest that continued treatment may not be beneficial to a given arm.

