4.1.6 Discontinuation of Investigational Product

An individual subject will not receive any further investigational product(s) if any of the following occur in the subject in question:

1. Withdrawal of consent from further participation in the study
2. Lost to follow-up
3. An AE that, in the opinion of the investigator or the sponsor, contraindicates further dosing
4. Subject experienced an AE that meets the criteria for a DLT during the DLT evaluation period (for Phase 1b and Phase 2; see Section 3.1.3.2 for definition of DLT)
5. Subject experienced an AE that meets the criteria for a DLT, except its occurrence is outside the DLT evaluation period (for Phase 1b and Phase 2; see Section 3.1.3.2 for definition of DLT)
6. Any AE that meets criteria for discontinuation as defined in Section 3.1.5
7. Subject is determined to have met one or more of the exclusion criteria for study participation at study entry and continuing investigational product(s) might constitute a safety risk
8. Pregnancy or intent to become pregnant
9. Subject noncompliance that, in the opinion of the investigator or sponsor, warrants withdrawal (eg, refusal to adhere to scheduled visits)

10. Initiation of alternative anticancer therapy including another investigational agent
11. Confirmed PD and all retreatment criteria in the setting of PD are not met (Section 3.1.2)

Subjects who are permanently discontinued from receiving investigational product(s) regardless of the reason (withdrawal of consent from further treatment, due to an AE, other), will be identified as having permanently discontinued treatment and will be followed for protocol-specified assessments including follow-up of any AEs unless consent is withdrawn specifically from further study participation; the subject is lost to follow-up; the subject starts alternative anticancer treatment; or the subject is enrolled in another clinical study. All subjects will be followed for survival until the end of the study. Subjects who decline to return to the site for evaluations should be contacted by phone every 3 months to assess for survival unless consent is withdrawn.

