4.2.3 Follow-up Period

[Table 4.2.3-1](#) shows all procedures to be conducted during the end of treatment visit and follow-up period. For subjects who complete all 12 months of treatment, the last dosing visit within the 12-month period is considered to be the end of treatment visit. Subjects who discontinue before 12 months will complete the end of treatment visit at the time the decision is made to discontinue treatment.

All subjects are to complete the end of treatment visit, all follow-up visits and be contacted for survival status in accordance with the Schedule of Study Procedures. However, if a subject discontinues from treatment and moves onto alternative anticancer treatment, the follow-up visits will no longer be required; however, survival follow-up assessments would be required as indicated in the Schedule of Study Procedures unless the subject withdraws consent for further survival follow-up. Survival follow-up will continue until the end of study as defined in Section [6.3](#).

After 90 days, only subjects with investigational product-related SAEs will continue to be followed for safety.

Table 4.2.3-1 Schedule of Follow-up Procedures (as of Amendment 6)

Study Period	Follow-up Period					
	EOT ^a	Day 30 post-EOT ± 3 Days	Day 60 post-EOT ± 3 Days	Day 90 post-EOT ± 7 Days	Q3M After Day 90 post-EOT up to Month 12 post-EOT ± 7 Days	Q6M After Month 12 post-EOT ± 14 Days
██████████	█			█		
Disease assessments						
Disease assessment by RECIST v1.1 (CT or MRI) ^b	X			X	X	X
Fresh tumor biopsy	X ^c					
Subsequent anticancer therapy		X	X	X	X	X
Survival status		X	X	X	X	X
Study procedures and examinations						
Physical examination	X	X	X	X		
ECOG performance status				X	X	X
Vital signs	X	X	X	X		
12-lead ECG ^d				X		
Assessment of AEs/SAEs	X	X	X	X		
Concomitant medications	X	X	X	X		
Laboratory tests						
Serum chemistry	X	X	X	X		
Hematology	X	X	X	X		
Thyroid function tests (TSH, free T3, free T4)	X	X	X	X		
Urinalysis	X	X	X	X		
Urine or serum pregnancy test	X					

Table 4.2.3-1 Schedule of Follow-up Procedures (as of Amendment 6)

Study Period	Follow-up Period					
	EOT ^a	Day 30 post-EOT ± 3 Days	Day 60 post-EOT ± 3 Days	Day 90 post-EOT ± 7 Days	Q3M After Day 90 post-EOT up to Month 12 post-EOT ± 7 Days	Q6M After Month 12 post-EOT ± 14 Days
[REDACTED]						
[REDACTED]					[REDACTED]	
[REDACTED]					[REDACTED]	
[REDACTED]		[REDACTED]			[REDACTED]	
[REDACTED]						
[REDACTED]					[REDACTED]	
[REDACTED]					[REDACTED]	

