5.4.1 Time Period for Collection of Adverse Events

AEs will be collected from time of signature of informed consent, enrollment, randomization, throughout the treatment period and including the follow-up period of 90 days after the last dose of MEDI4736 and tremelimumab.

SAEs will be recorded from the time of informed consent signature through 90 days after the last dose of MEDI4736 and tremelimumab.

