PD-L1 expression is around 40%, approximately 18 evaluable subjects with high PD-L1 expression for either arms A or B will be expected. The probability of observing at least 1 responder out of 18 evaluable subjects will be at least 90% if the response rate is at least 15%. Additional subjects with high PD-L1 expression may be enrolled in order to further evaluate this population.

With approximately 45 evaluable subjects for Arm A and 22 evaluable subjects for Arm C, the study has 85% power to detect a difference of 35% vs 10% in the response (or PFS-6) rates assuming a 1-sided $\alpha = 0.10$ between the combination arm and the tremelimumab monotherapy arm.

Arm D

It is planned to enroll 25 subjects in Arm D.

Arm E (as of Protocol Amendment 6)

Approximately 40 additional subjects who are biomarker positive will be assigned to Arm E. Assuming 10% of the subjects are not evaluable for response or drop-out without PFS event before 6 months, approximately 36 evaluable subjects for Arm E are expected. The sample size determination is based primarily on the consideration of providing the estimation with reasonable precision. As shown in Table 2.4.2-2, when the ORR is expected to be in the 28% to 39% range, a total of 36 subjects would provide a width of 12% to 14% between the observed point estimator and its lower limit of the exact 90% CI. If 19 of 36 subjects have PFS \geq 6 months, the PFS-6 will have an estimate of 53% with a 90% CI of (39%, 67%). Assuming that PFS follows an exponential distribution, the PFS-6 of 53% will correspond to a median PFS of 6.6 months, which is a 50% increase from the 4.4 months observed for ramucirumab plus paclitaxel in subjects with metastatic gastric or GEJ adenocarcinoma following disease progression on first-line platinum- and fluoropyrimidine-based combination therapy in the RAINBOW study.

Table 2.4.2-2 Observed ORR/PFS-6 with 90% CI (Arm E)

N	Number of Subjects with OR	ORR	2-sided Exact 90% CI	
36	10	28%	16%	43%
36	14	39%	25%	54%

N	Number of Subjects with PFS at 6 Months	PFS6	2-sided 90% CI	
36	19	53%	39%	67%

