3.8 Safety Analyses

In Phase 1b, the number of DLTs that are identified in the DLT Evaluable Population during the DLT evaluation period will be summarized and listed. Safety data including AEs, SAEs, laboratory parameters, ECGs, vital signs and ECOG performance status, will be summarized in the As-treated population by treatment group, pooled dose groups and overall.

Repeated or unscheduled tests will not be summarized for each scheduled visit, but will be included for summaries of “worst-case” on treatment values and shift-table analyses. “Worst-case” on treatment (i.e. maximum or minimum on-treatment value depending on the direction of an adverse effect) is defined as the nadir and/or zenith including any scheduled and unscheduled post-baseline assessments that occur through the last assessment on-treatment. The last assessment on-treatment is defined as the last visit with a non-missing observation that occurred up till 90 days (+7 days to allow for a visit window) following the last dose of study treatment (if safety follow-ups are performed till 90 days after the last dose), or till the initiation of the subsequent anticancer therapy (excluding palliative radiotherapy), whichever occur first.

If the number of subjects with available data is less than 10% of the total number of subjects in the As-treated Population for overall summary for the dose escalation phase, or for each cohort in the dose expansion phase at a scheduled time of evaluation, no summary statistics will be presented at that time point, unless otherwise indicated.

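### The Phase 2 33% pause prompt counts only treatment-period events, so a first DLT-type event after end of treatment is recorded but not counted

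*Protocol*

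**What the plan says.** Protocol section 3.1.4 (Phase 2) sets the prompt: "If during the treatment period, $\geq 33\%$ of subjects experience safety events meeting DLT criteria, even if outside of the DLT evaluation period". The Synopsis repeats it and states the consequence: "even if outside of the DLT evaluation period, enrollment may be paused and study data will be reviewed".

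Protocol section 4.2.3 places the end of treatment visit. For early stoppers: "Subjects who discontinue before 12 months will complete the end of treatment visit at the time the decision is made to discontinue treatment". For those who complete 12 months, "the last dosing visit within the 12-month period is considered to be the end of treatment visit".

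Protocol section 4.1.6 makes an event of this kind a reason to stop dosing. Criterion 4 covers the DLT window and criterion 5 extends it: "Subject experienced an AE that meets the criteria for a DLT, except its occurrence is outside the DLT evaluation period".

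Protocol section 5.4.1 collects adverse events "throughout the treatment period and including the follow-up period of 90 days after the last dose of MEDI4736 and tremelimumab". SAP section 3.8 uses a similar window for worst-case on-treatment values: up to 90 days (+7) after the last dose, "or till the initiation of the subsequent anticancer therapy (excluding palliative radiotherapy), whichever occur first".

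**The concern.** The prompt deliberately reaches beyond the DLT window, which suggests that late toxicity was in mind. The Amendment 1 summary (Protocol section 9.1) points the same way: it lists a revision of the stopping rules for severe late immune-related toxicities. Yet the count remains tied to the treatment period, while collection runs to 90 days after the last dose.

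Consider a subject who stops for progression and later has a first event meeting DLT criteria. The event is recorded, but on the readable text that subject never enters the numerator. Leaving such subjects out can only lower the observed percentage and delay the prompt. It is the only readable Phase 2 enrollment-pause rule with a numeric rate, so its numerator should be complete.

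**Working it through.** **1. The windows side by side.**

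| Item | Source | Reaches to |
|---|---|---|
| 33% count | Protocol 3.1.4, Synopsis | treatment period |
| End of treatment visit | Protocol 4.2.3 | decision to stop, or last dosing visit for completers |
| AE and SAE collection | Protocol 5.4.1 | 90 days after last dose |
| Worst-case on-treatment values | SAP 3.8 | 90 days (+7) after last dose, or next anticancer therapy |

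Section 5.4.1 names the treatment period and the 90-day follow-up separately, so the first does not naturally contain the second.

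**2. Who falls in the gap.** An event that itself ends dosing (section 4.1.6, criteria 4 and 5) precedes the decision to stop and is counted. So is any other event between the last dose and that decision. What remains is a subject who stops for another reason and has a first qualifying event later. Completers add almost nothing: their late events come about a year after entry, when there may be little or no enrollment left to pause.

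**3. Size.** The plan gives no operating characteristics for the prompt, so there is no figure to reproduce. The following is an illustration.

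From the documents: the 33% threshold, and Arm E's size (SAP section 2.4.2: "Approximately 40 additional subjects who are biomarker positive will be assigned to Arm E").

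Assumed:
- p is the true share with a qualifying event by 90 days after the last dose; f is the share of affected subjects whose first event comes only after end of treatment.
- The prompt applies to Arm E alone, with uniform accrual over 12 or 18 months.
- Treatment time is exponential with median 3 months, capped at 12.
- On-treatment onset is uniform over the first 3 months, or over treatment time if shorter. Late onset is uniform over the 3 months after end of treatment.
- The count is checked at each enrollment with n = 20 to 39 already enrolled, and the prompt fires if it is at least 0.33n.

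The expected number of uncounted subjects is 40 × p × f. At p = 0.40 and f = 0.02 this is 0.32; at p = 0.40 and f = 0.05 it is 0.8; at p = 0.45 and f = 0.10 it is 1.8.

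Probability of firing before the last enrollment, treatment-period count → count including the 90 days (20,000 simulated trials per setting):

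| Accrual | p | f = 0.02 | f = 0.05 | f = 0.10 |
|---|---|---|---|---|
| 12 months | 0.40 | 0.814 → 0.827 | 0.772 → 0.809 | 0.704 → 0.782 |
| 12 months | 0.45 | 0.922 → 0.930 | 0.899 → 0.923 | 0.853 → 0.909 |
| 18 months | 0.40 | 0.852 → 0.865 | 0.819 → 0.857 | 0.752 → 0.842 |
| 18 months | 0.45 | 0.944 → 0.951 | 0.927 → 0.949 | 0.885 → 0.942 |
| 12 months | 0.20 | 0.072 → 0.075 | 0.058 → 0.066 | 0.044 → 0.058 |
| 18 months | 0.20 | 0.090 → 0.097 | 0.076 → 0.090 | 0.060 → 0.085 |

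At p = 0.40-0.45 the gain is about 1 point (f = 0.02), 2-4 points (f = 0.05) or 6-9 points (f = 0.10). At p = 0.20 the extra firing is about 0.3 to 2.5 points.

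**4. These are upper bounds for the proposed wording.** The simulation does not stop counting at subsequent anticancer therapy. If half of the late events followed new therapy (an assumption), the gain at p = 0.40, f = 0.05 and 12-month accrual would be about 2 points instead of 4.

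**The case against.** The strongest reply is that this is a preference and not a defect. The prompt forces nothing. Section 3.1.4 also requires continuous safety monitoring, SAEs are reported within 24 hours (section 5.5), hepatic events can go to a safety committee (section 5.6.2), and the sponsor may suspend at any time (section 4.4). Late events are therefore seen. The group is narrow too: subjects may stay on treatment until progression is confirmed at least 4 weeks later (section 3.1.2.4), and reinduction, crossover and retreatment are themselves treatment periods in the schedule tables. Phase 1b saw no DLTs in 6 subjects, and at a 40-45% rate the existing prompt already fires in about 70-94% of simulated trials.

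All of this stands and limits the weight of the point. It does not close the gap, because none of these safeguards puts a late event into the 33% count.

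Two stronger readings are tempting and should be resisted. A reader might infer from section 4.2.3 that, for completers, the entire 90 days lies outside the count. That section places the end of treatment visit; it does not define when the 12-month period ends. The last scheduled visit is Day 351 (Table 4.2.2-2), so some days after the last dose may still fall within the period. A reader might also judge the size from a single look at all 40 Arm E subjects with full follow-up, which shows a larger difference. By then no planned Arm E enrollment is left to pause, so that comparison does not describe what the prompt does.

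**Conclusion.** The point holds as a modest improvement to consider. On the readable text, a first qualifying event after end of treatment but within the 90-day window is collected and left out of the 33% count. Those affected are mainly subjects who stop for progression while others are still being enrolled.

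This rests on a literal reading. Much of the regimen text and the interim-analysis section (4.8.8) cannot be read and might say more. It would be wrong to infer that late toxicity goes unmonitored or that a stated limit is breached.

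The documents give no event rate, late share, accrual pattern or treatment time, so the size cannot be derived from them. The 1-9 point range is an upper bound under the stated assumptions; the true effect is probably small.

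**What to change.** In Protocol section 3.1.4 and the Synopsis, replace the treatment-period limit with: *during the treatment period, or after it until the earlier of 90 days after the last dose and the start of subsequent anticancer therapy (palliative radiotherapy excepted)*. Leave the DLT criteria, the exclusion of toxicity plainly due to disease or another cause (section 3.1.3.2), the 33% threshold and the discretionary review as they are. If the sponsor already intends the wider window, this wording makes that explicit.

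The cost is one phrase in two places, with no new data collection. There are two downsides. The prompt fires slightly more often when toxicity is acceptable: at most about 2.5 points at an assumed 20% rate. Late Grade 3 or higher events must also be attributed against progression, and those without a clear other cause would count. Ending the count at subsequent anticancer therapy limits that burden.
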